1.1.1 Evidence

Asymptomatic carotid artery stenosis, per definition, can be found only in the context of screening examinations. Due to the lack of systematic screening examinations valid data about prevalence is not known. It is estimated that the prevalence of asymptomatic carotid artery stenoses $\geq 50\%$ is around 2-8%, and of stenoses $\geq 80\%$ around 1-2% [9]. Moderate to severe ($\geq 70\%$) asymptomatic stenosis of the extracranial carotid artery leads to an increased rate of stroke of approximately 11% in five years [8, 12]. Patients with asymptomatic carotid stenosis, however, are at also higher risk of non-stroke vascular events. The estimated annual risks of such events in patients with asymptomatic stenosis are 7% for coronary ischemic event and 4-7% for overall mortality [15].

1.1.2 Role of conservative treatment

Medical management of patients with asymptomatic carotid stenoses consists of risk factor modification, antiplatelet medication and careful monitoring of progression or hemodynamic relevance by ultrasound. Although no primary prevention trials specifically focusing on patients with asymptomatic carotid stenosis have been done, these treatment regimens have been the standard therapy for asymptomatic carotid stenoses in the past and many treatment guidelines still recommend them as therapy of choice if surgical treatment cannot be provided with morbidity and mortality-rates below 3% [6].

1.1.3 Role of carotid endarterectomy

The Asymptomatic Carotid Surgery Trial (ACST) and the smaller Asymptomatic Carotid Atherosclerosis Study (ACAS) studied the role of CEA in nearly 5,000 patients with asymptomatic carotid stenoses (no stroke or stroke-like symptoms within the previous 6 months) [7-8]. A recent metaanalysis included three trials with a total of 5,223 patients. In these trials, the overall risk of perioperative stroke or death was 2.9%. For the

outcome of perioperative stroke or death or any subsequent stroke, patients undergoing CEA fared better than those treated medically (relative risk (RR) 0.69, 95% confidence interval (CI) 0.57 to 0.83). Similarly, for the outcome of perioperative stroke or death or subsequent ipsilateral stroke, there was benefit for the surgical group (RR 0.71, 95% CI 0.55 to 0.90). For the outcome of any stroke or death, there was a non-significant trend towards fewer events in the surgical group (RR 0.92, 95% CI 0.83 to 1.02)[4]. The general applicability of these findings has been questioned because morbidity and mortality rates exceeding 3% have been reported in general surgical practice under non-trial.

1.1.4 Role of carotid artery stenting

During the past decade, stent-protected angioplasty has been introduced as an alternative treatment for carotid stenoses. Several studies have investigated its efficacy in preventing further strokes in symptomatic carotid stenoses [3, 16], information on its efficacy in asymptomatic carotid stenosis was limited to self-reported uncontrolled case-series and registries [20, 22]. Recently the CREST trial has been published, including a substantial proportion of asymptomatic patients [2]. For the entire proportion of 2.502 patients there was no difference between CAS and CEA regarding the primary composite end point stroke, myocardial infarction, or death from any cause during the periprocedural period or any ipsilateral stroke within 4 years after randomization. This was not influenced by the symptomatic-status. However the subgroup analysis for asymptomatic patients was not powered to proof the equivalence of CAS and CEA in those patients and CREST did not have a medical arm.

1.2 Trial rationale/ justification

There is substantial and ongoing uncertainty in the choice of treatment for patients with asymptomatic carotid stenoses. Although a benefit has been demonstrated for surgery under well-controlled trial conditions, the applicability of these findings to the general population is an ongoing controversy [4]. Specifically two major criticisms exist: Firstly, the absolute and relative risk reduction of CEA over conservative treatment is rather small. Consequently, the numbers needed to treat (NNT) are high. Secondly, the majority of conservatively treated patients in ACAS and ACST was included more than 10 years ago and was not treated according to today's recommendations and guidelines. It has been argued that these trials should be repeated in the light of recent advances in medical treatment [5].

Only limited information on safety and efficacy of CAS is available for asymptomatic stenoses. Most of the data derive from the SAPHIRE study, which included less than 150 asymptomatic patients per study arm. The results suggesting superiority of CAS over CEA are driven by the cardiovascular contribution to the endpoint, not by stroke. Potential advantages of stenting are shorter target vessel occlusion times, lack of wound healing problems, shorter hospital stay and usually the procedure is performed without general anesthesia. Despite the lack of evidence several thousand procedures are done every year. To clarify the role of CAS compared to CEA and modern medical treatment a large-scale randomized trial is clearly needed. The European Stroke Initiative (EUSI) Recommendations for Stroke Management support this and suggest that CAS is not routinely recommended for patients with asymptomatic carotid stenosis. It should be considered in the context of randomized clinical trials only [19].

The results of this trial are expected to be the base for defining a proven standard for the treatment of asymptomatic carotid artery stenosis and would have wide impact on managing this disease.

1.3 Benefit / risk assessment

The benefit from every treatment modality is the proposed reduction of future cerebro- and also cardiovascular events. However, each treatment arm carries specific risks. Risks from the conservative treatment are mainly due to possible side effects of the used medication. Most feared risk of both CAS and CEA is the risk of periprocedural stroke. Differences between the risk of CAS and CEA are based on technical details. CEA is usually performed under general anesthesia, which might contribute to the procedure related complication rate, up to now only a few centers offer local anesthesia as an alternative. In contrast CAS is generally performed under local anesthesia, general anesthesia is only required in patients with poor cooperation. CAS always needs interventional angiography, which increases the risk of stroke by 0.1–0.3% [7]. Current experience suggests that CAS without embolic protection devices causes more microembolic events than does CEA and these events seem to be associated with an increased risk of postinterventional DWI lesions, however the clinical impact of these lesions is still under discussion [13]. Although CAS causes fewer cranial nerve lesions, it might be associated with more-frequent restenoses than CEA.

To minimize these risks every individual in the trial will be treated by named experts and a close monitoring for such events will be done. In addition both endarterectomy and

stenting will be done only by certified physicians with a high level expertise and continuous quality control. For any treatment modality quality committees are defined. These committees define the rules for the treatment and the quality control criteria (see Appendix).

2 TRIAL OBJECTIVES AND ENDPOINTS

2.1 General aim / primary objective

The objective of this study is to compare up-to-date medical (conservative) treatment including life-style modification with carotid artery stenting and carotid endarterectomy in addition to those conservative treatments in treatment of individuals with asymptomatic atherosclerotic carotid artery stenoses.

OLD: Therefore on the first level, a superiority trial of intervention (CAS or CEA) versus state of the art conservative treatment is designed. In case of superiority of both interventions, a non-inferiority endpoint will be tested between CAS and CEA.

NEW: Therefore on the first level, a superiority trial of interventions versus best medical treatment (BMT) is designed. Both interventional treatment-groups (CEA and CAS) will be compared with the BMT patients of the specific substudy. In addition data from the CEA and CAS-groups will be compared in an explorative manner by an indirect treatment comparison. This data can also be used for a combined analysis with other international trials comparing these treatment modalities (e.g. ACST2).

2.2 Assessment of safety

Safety is assessed as the rate any stroke within 30 days of treatment, and death from any cause within 30 days. This endpoint has been used in many trials concerned with treatment of carotid stenoses [7-8, 10, 16].

2.3 Composite primary efficacy endpoint

The primary efficacy endpoint is the cumulative rate of any stroke or death from any cause within 30 days plus ipsilateral ischemic stroke within 5 years of follow up.

The primary effect expected from surgery or stenting is to reduce hemodynamic or thromboembolic ischemia of ipsilateral brain tissue. The clinically relevant figure is the sum of periprocedural complications and ipsilateral ischemia during a longer period. Conservative treatment is expected to go along with low 30-day complication rates but higher long-term ipsilateral ischemia rates. The reverse is to be expected with surgery

and stenting. The efficacy endpoint takes into account both components. This endpoint has been used in many previous carotid stenosis trials [7-8, 16].

2.4 Secondary and tertiary outcomes

Secondary and tertiary efficacy endpoints are single components of the primary endpoint, cardiac events, technical failures and observations at different time points. These are described in detail in chapter 6.3.

3 TRIAL DESIGN

OLD: SPACE-2 is a randomized, controlled, open, multi-center study with three parallel groups:

Best medical treatment (BMT)

Carotid endarterectomy (CEA) + BMT

Carotid artery stenting (CAS) + BMT

A hierarchical study protocol has been developed with a superiority design of intervention vs. conservative treatment. In case superiority for CAS and CEA is established, a non-inferiority comparison between the two interventions will be performed.

NEW: SPACE-2 is a randomized, controlled, open, multi-center study with two parallel substudies:

- SPACE2a: CEA vs. BMT
- SPACE2b: CAS vs. BMT

Primary aim of the study is to compare BMT with any type of intervention (CEA or CAS). In addition, data from the CEA and CAS-groups will be compared in an explorative manner. In order to analyze the effect between the two interventional methods, an indirect treatment comparison will be applied [17].

All patients are treated with a best medical treatment regimen tailored to their individual risk factor profile consisting in treatment of risk factors, lipid-lowering and anti-platelet medication. Rules for the BMT will be formulated by the BMT-subcommittee and are an appendix to this protocol.

The overall duration of the trial is expected to be approximately 9 years. Recruitment of subjects will start in October 2008. The actual overall duration of recruitment may vary.

4 SELECTION OF SUBJECTS

4.1 Number of subjects

OLD: As calculated in section 9.1 'Sample Size Calculation', 3,640 subjects should be enrolled in the clinical trial, 540 to the BMT-Arm, 1,550 to the surgical and 1,550 to the stenting-group.

NEW: As calculated in section 9.1 'Sample Size Calculation', 1636 subjects should be enrolled in the group sequential clinical trial with one interim analysis, 818 patients per arm. This is the case for SPACE2a comparing CEA with BMT and for SPACE2b comparing CAS with BMT. Both trials would require a total of 3,272 patients.

Recruitment and treatment of subjects should be performed in around 100 trial centers. The minimum / maximum number of subjects per trial centre should be 10/200.

4.2 General criteria for subjects' selection

In daily clinical practice most asymptomatic carotid stenoses are discovered by extracranial ultrasound techniques performed for screening purposes in patients with vascular disease in other vascular territories. Only some stenoses are diagnosed by extracranial MRA or due to cervical bruits. Due to the ultrasound-based screening procedure used in SPACE-2, the study population should closely resemble the population with asymptomatic carotid stenoses in general.

4.3 Inclusion criteria

Subjects meeting all of the following criteria will be considered for admission to the trial:

Males or females aged ≥ 50 and ≤ 85 years

Carotid artery stenosis of $\geq 70\%$ following ultrasound criteria

No stroke or stroke-like symptoms due to the stenosis within the last 180 days

Stenosis treatable with CEA **or** CAS

Ability of the patient for follow-up examinations

Personally written informed consent from the patient

For women with childbearing potential, adequate contraception

4.4 Exclusion criteria

Subjects presenting with any of the following criteria will not be included in the trial:

Non-atherosclerotic stenosis (e.g. dissection, floating thrombus, fibromuscular dysplasia)

Stenosis following radiotherapy

Previous CEA or CAS in the artery to be randomized

Additional higher grade intracranial or intrathoracic stenosis (tandem stenosis)

Intracranial bleeding within the last 90 days

Known intracranial angioma or aneurysms

Severe pre-existing disability (modified Rankin scale more than one)

Contraindications for heparin, aspirin, clopidogrel or contrast media

OLD: Indication for anticoagulation with Phenprocoumon (Marcumar®) or Warfarin

NEW: Deleted

Life expectancy of less than 5 years

Recent history of malignoma

Major surgery (with exception of trial related procedures) planned within 8 weeks after randomization

No subject will be allowed to enroll in this trial more than once.

4.5 Criteria for withdrawal

4.5.1 Withdrawal of subjects

A subject may be withdrawn from all trial related procedures (including follow-up visits) for the following reasons:

at his/her own request or at request of his legal representative

non-adherence to the trial-related requirements, which may (have) influence(d) the validity of the trial data

If, in the investigator's opinion, continuation of the trial would be detrimental to the subject's well-being, e.g. if a patient was randomized into the BMT arm and suffers ipsilateral neurological symptoms, patient treatment based on actual guidelines either with CEA or CAS

Occurrence of exclusion criteria

If, in the investigator's opinion, protocol violations caused by the subject would lead to invalid data (e.g. non-compliance with planned study procedures).

The Executive Committee (see chapter 10.2) decides about withdrawal of subjects from trial treatment in case of occurrence of criteria mentioned above. A withdrawn patient will be treated as censored at time of leaving the study.

In all cases, the reason for withdrawal must be recorded in the CRF and in the subject's medical records. In case of withdrawal of a subject at his/ her own request, the reason should be asked for as extensively as possible and documented. All efforts will be made to follow up the subject and, all examinations scheduled for the final trial day will be performed as far as possible on all subjects and documented. All ongoing Adverse Events (AEs) / Serious Adverse Events (SAEs) of withdrawn subjects have to be followed up until no more signs and symptoms are verifiable or the subject is on stable condition.

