9.3 Definition of trial population to be analyzed

The primary analysis will be intention-to-treat (ITT). In addition, due to the nature of a non-inferiority study, a per-protocol (PP) analysis will also be performed. The PP includes all patients without major protocol deviations. The following are considered major protocol deviations:

- Not meeting one or more of the Inclusion Criteria and/or falling into one or more of the Exclusion Criteria
- Not finishing the allocated therapy (change of treatment group)
- Operation or Stenting done by an non-certified interventionalist or using non-certified material
- Endpoint event between randomization and treatment (if allocated to CEA or CAS)

In case of problems with the decision if a protocol violation is major, the Endpoint Evaluation Committee (see page 40) is responsible for the allocation; this will be done prior the unblinding of the data.

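### Exclusion criteria that appear after randomisation can end follow-up with censoring (section 4.5.1) and remove patients from the per-protocol set (section 9.3), which conflicts with the ITT primary analysis

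*Protocol*

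**What the plan says.** Four statements in Protocol section 4.5.1 bear on this.

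- Scope: "A subject may be withdrawn from all trial related procedures (including follow-up visits) for the following reasons". One reason listed is "Occurrence of exclusion criteria".
- Decision: the Executive Committee "decides about withdrawal of subjects from trial treatment in case of occurrence of criteria mentioned above". This sentence speaks of trial treatment, not of all procedures.
- Analysis: "A withdrawn patient will be treated as censored at time of leaving the study".
- Follow-up: "All efforts will be made to follow up the subject", with the final-day examinations to be done as far as possible.

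Section 9.3 makes ITT the primary analysis. It defines a PP set without major deviations, the first of which is "Not meeting one or more of the Inclusion Criteria and/or falling into one or more of the Exclusion Criteria". It gives no date by which the criterion must have been present and no rule on the source of the evidence.

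The exclusion criteria in section 4.4 include "Additional higher grade intracranial or intrathoracic stenosis (tandem stenosis"), known intracranial angioma or aneurysm, recent intracranial bleeding, recent malignancy and a life expectancy under 5 years. On imaging, section 1.3 says "CAS always needs interventional angiography". The visit schedule contains ultrasound but no angiography for any arm, so a patient allocated to best medical treatment (BMT) has no planned angiography.

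**The concern.** In an ITT analysis, eligibility is settled at randomisation, and what happens afterwards is outcome or course of disease. Here an entry criterion stays active after randomisation and can take a patient out of follow-up. If the reason relates to prognosis, the censoring is informative and the Cox comparison no longer estimates the effect in all randomised patients. If the reason is also detected at different rates in the two arms, the loss is unbalanced.

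Both conditions are plausible. Intracranial bleeding, malignancy and short life expectancy can all arise after entry. An intrathoracic tandem stenosis may come to light at the stent procedure, and an aneurysm seen there becomes a known one; the same lesion in a BMT patient may never be looked for. The trial is open, and no blinding is stated for the committee that decides on withdrawal. Early withdrawal also cuts short the 5-year secondary endpoints, such as any stroke or vascular death.

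**Working it through.** **Step 1. Set the rules side by side.**

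| Question | Statements that keep the patient in | Statements that take the patient out |
|---|---|---|
| Does follow-up continue? | 4.5.1: efforts to follow up; final-day examinations where possible | 4.5.1: withdrawal covers follow-up visits |
| Do later events count? | 9.3: ITT is primary | 4.5.1: censored on leaving the study |
| What is withdrawn? | 4.5.1: trial treatment (committee sentence) | 4.5.1: all trial procedures (opening sentence) |
| Which eligibility facts matter for PP? | – | 9.3: any exclusion criterion, no cut-off date |

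On the left-hand reading, withdrawal stops treatment only and nobody is censored. On the right-hand reading, events after withdrawal are lost or ignored. The protocol supports both.

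**Step 2. Reproduce the planned size, to see how many events carry the comparison.** Inputs from sections 4.1 and 9.1: BMT hazard 0.01 per year, hazard ratio (HR) 0.50, two-sided 5%, power 80%, accrual 5 years plus 3 years of follow-up, 818 per arm.

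- Schoenfeld: 4 × (1.960 + 0.842)² / (ln 0.50)² = 65.3, so 66 events.
- Event probability with uniform accrual: p(λ) = 1 − (e^(−3λ) − e^(−8λ)) / (5λ). This gives 0.0534 for λ = 0.01 and 0.0271 for λ = 0.005, mean 0.0403.
- N = 66 / 0.0403 ≈ 1,640, against the stated 1,636.

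The comparison rests on about 66 events, so a few selective losses are not trivial.

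**Step 3. Illustrate the mechanism.** The documents give no frequency of exclusion findings after randomisation and no risk for such patients. Assume that a fraction f of the intervention arm is removed at the start, that these patients carry r times the risk of the others, and that nobody is removed from BMT.

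- 5-year BMT risk: p = 1 − e^(−0.05) = 4.88%, or 818 × 0.0488 = 39.9 events per arm if there is no treatment effect.
- Risk among those left in the intervention arm: p′ = p / (1 − f + f·r).
- Apparent HR = ln(1 − p′) / ln(1 − p).
- Chance of a significant result favouring intervention: Φ(√(d/4) × |ln HR| − 1.96), with d the events remaining.

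| f | r | Patients removed | Events lost | Apparent HR (true 1.00) | One-sided error (nominal 2.5%) |
|---|---|---|---|---|---|
| any | 1 | 818·f | – | 1.00 | 2.5% |
| 1% | 2 | 8.2 | 0.8 | 0.99 | 2.8% |
| 1% | 3 | 8.2 | 1.2 | 0.98 | 3.1% |
| 3% | 3 | 24.5 | 3.4 | 0.94 | 4.5% |
| 3% | 5 | 24.5 | 5.3 | 0.89 | 7.2% |
| 5% | 5 | 40.9 | 8.3 | 0.83 | 12.1% |

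Worked line for the last row: p′ = 0.0488 / 1.20 = 0.0406; HR = 0.0415 / 0.0500 = 0.83; d = 39.9 + 818 × 0.95 × 0.0406 ≈ 71.5; √(71.5/4) × |ln 0.83| = 0.79; Φ(0.79 − 1.96) ≈ 0.12.

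The model is deliberately extreme: all removals fall in one arm and all events of the removed patients are lost. Removals in the BMT arm at similar risk would offset the shift.

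**The case against.** The case for leaving the text alone has several parts.

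- **The rule is optional and general.** It says patients may be withdrawn, needs a committee decision and covers every arm. This stands. A reader might infer that high-risk patients are removed from the stent arm only; the documents do not say so.
- **Angiography is not shown to be the only route.** A reader might infer that several criteria can be found only that way. The screening ultrasound in section 5.2.5 includes the intracranial circulation, ultrasound is repeated at follow-up in all arms, and section 1.3 mentions angiography for its stroke risk without saying which vessels are shown. What remains is a plausible difference in detection, clearest for intrathoracic stenosis.
- **Some criteria do not fit.** Stenosis below 70% fails an inclusion criterion that is defined by ultrasound. The Rankin criterion concerns disability present before entry. Previous surgery or stenting refers to the artery at entry. None of these supports the point. A haemorrhagic stroke within 30 days is already a primary event, so censoring after it does not alter a time-to-first-event analysis.
- **Other provisions point towards retention.** Section 5.2 counts events before treatment in the allocated group, and inability to treat with the allocated method is recorded as technical failure, a secondary endpoint. This suggests an intention to keep such patients, but it does not override the censoring sentence.
- **PP is supplementary.** A stent patient left untreated because of an angiographic finding already leaves the PP set for not finishing the allocated therapy. That is correct and limits the added effect of the eligibility clause there.

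The promise to attempt follow-up does not settle the matter, because the censoring sentence would set aside later events even if they were collected.

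**Conclusion.** The point holds as a fault in the written rules. Sections 4.5.1 and 9.3 let exclusion criteria act after randomisation, and 4.5.1 contradicts itself on whether such patients are followed and counted. Followed literally, it permits prognosis-related censoring inside an analysis labelled ITT, and that censoring may differ by arm. This is more than detail left to an analysis plan, because the protocol itself fixes the censoring.

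The size is unknown. Under the assumed removals (1% to 5% of one intervention arm, 2 to 5 times the risk of the others), a true HR of 1.00 would appear as 0.99 to 0.83. With removed patients at average risk there is no shift. The lower end is negligible; the upper end would matter.

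A reader might conclude that the primary result is biased in favour of stenting. The documents do not establish that: it depends on how often the ground is used, in which arm, and whether event collection stops. The rule should be corrected because it leaves the door open and is cheap to close.

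**What to change.** **Section 4.5.1:** state that an exclusion criterion that occurs or is discovered after randomisation does not end follow-up and does not lead to censoring in the ITT analysis. Reconcile the opening sentence, the committee sentence, the censoring sentence and the follow-up sentence accordingly. Leave decisions on trial treatment untouched; deleting the ground outright would reach into those decisions and is not needed.

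**Section 9.3:** limit PP eligibility violations to facts present before randomisation and ascertainable in the same way in both arms. Report by arm the patients in whom a criterion emerged later.

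**Cost:** an amendment of about two sentences. A few more patients stay in visits that are already scheduled, and the PP set keeps a few patients whose exclusion criterion was found later.

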6.3 Evaluation of efficacy

6.3.1 Primary endpoint

The primary efficacy endpoint is the cumulative rate of any stroke (ischemic or haemorrhagic) or death from any cause within 30 days plus ipsilateral ischemic stroke within 5 years of follow up.

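### Section 4.5.1 lets BMT patients with ipsilateral symptoms short of stroke leave follow-up and be censored, which is risk-related and conflicts with the ITT primary analysis

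*Protocol*

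**What the plan says.** Section 4.5.1 opens with "A subject may be withdrawn from all trial related procedures (including follow-up visits) for the following reasons". The reasons include the subject's own request, non-adherence, the later appearance of an exclusion criterion, and the investigator's view that continuing would harm the subject. The last carries the only worked example, "e.g. if a patient was randomized into the BMT arm and suffers ipsilateral neurological symptoms", followed by CEA or CAS according to guidelines. The section then fixes the analysis rule: "A withdrawn patient will be treated as censored at time of leaving the study".

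Other text points a different way:

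- In the same section, the Executive Committee "decides about withdrawal of subjects from trial treatment in case of occurrence of criteria mentioned above", which concerns treatment and not follow-up.
- The same section also says, with a qualifier on feasibility, "All efforts will be made to follow up the subject and, all examinations scheduled for the final trial day will be performed".
- Section 5.5 has the same BMT patients considered for CEA or CAS and mentions no withdrawal.
- Section 9.3 makes ITT the primary analysis and lists a change of treatment group among the per-protocol exclusions.

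The long-term part of the primary endpoint (section 6.3.1) is "plus ipsilateral ischemic stroke within 5 years of follow up". Section 6.1 requires a deficit of more than 24 hours for a stroke. Section 9.4 specifies a Cox model.

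**The concern.** The Cox comparison assumes that a patient's censoring carries no information about later risk. A BMT patient with a transient ipsilateral deficit has had no primary event, but has had symptoms in the territory where the long-term endpoint is counted. If that patient is withdrawn and censored, a later ipsilateral ischemic stroke does not enter the analysis. The example names BMT only, so the loss it describes falls on the control arm and works against showing a benefit of intervention.

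That such patients are at higher risk is an inference. The protocol gives no stroke rate after such symptoms. It does call the benefit of CEA established in symptomatic disease and less well established in asymptomatic disease (section 1.1), and it bars entry after symptoms from the stenosis within 180 days (section 4.3).

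The comparison would also depart from ITT, because a crossover that section 9.3 treats as a per-protocol matter could end a patient's contribution to the primary analysis. An SAP cannot recover events from visits that the protocol allowed to stop.

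**Working it through.** **Inputs.** BMT event rate 0.01 per year, HR 0.50, two-sided 5%, power 80%, and accrual 5 + follow-up 3 years for the group sequential design (section 9.1); 818 patients per arm (section 4.1). The number allocated equals the number analyzed (protocol summary), so there is no dropout allowance.

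**Reproducing the plan's figure.** Schoenfeld events: 4(1.960 + 0.842)² / (ln 0.50)² = 65.3. With uniform accrual over a years and minimum follow-up f, the event probability is p(λ) = 1 − [exp(−λf) − exp(−λ(a+f))] / (λa). For a = 5 and f = 3, p(0.01) = 0.0534 and p(0.005) = 0.0271, with mean 0.0402. This gives N = 1,624 for a fixed design. The stated 1,636 is 0.7% higher, a plausible O'Brien-Fleming inflation. Section 9.1 attaches 1,624 to accrual 3 + follow-up 5, where the same formula gives 1,378. That is a separate matter, but it is why both layouts are shown below.

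**Expected events at 818 per arm (5 + 3).** BMT 818 × 0.0534 = 43.7; intervention 818 × 0.0271 = 22.2; total 65.9.

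**Effect of the censoring rule.** Let q be the share of BMT primary events lost because the patient was censored first. This is an assumption. The BMT hazard becomes 0.01(1 − q), the HR becomes 0.50/(1 − q), and power = Φ(½√D·|ln HR| − 1.96), where D is the expected number of events.

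| q | BMT events lost (5 + 3) | HR | D (5 + 3) | Power (5 + 3) | Power (3 + 5) |
|---|---|---|---|---|---|
| 0 | 0 | 0.50 | 65.9 | 80% | 86% |
| 5% | 2.1 | 0.53 | 63.7 | 73% | 79% |
| 10% | 4.3 | 0.56 | 61.6 | 64% | 71% |
| 20% | 8.5 | 0.63 | 57.3 | 43% | 49% |

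A log-rank simulation of the 3 + 5 layout, with BMT patients censored shortly before the lost stroke, gives 85%, 69% and 47% at q = 0, 10% and 20%.

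**What the fix would recover.** Under ITT these patients may still cross over to CEA or CAS, which would prevent some of the strokes. If crossover halved their risk (an assumption, borrowing the planning HR), the fix would still forgo q/2 of the BMT events. In the 5 + 3 layout:

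| q | Power if censored | Power with fix, crossover halving risk | Difference |
|---|---|---|---|
| 10% | 64% | 73% | 9 points |
| 20% | 43% | 64% | 21 points |

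**The case against.** The strongest defense is that nothing obliges anyone to withdraw these patients. The list says that a subject may be withdrawn, censoring applies on leaving the study and not on changing treatment, follow-up efforts are required, and sections 5.5 and 9.3 imply that a crossed-over patient stays in the ITT set. This stands against a stronger reading that a reader might infer: that every symptomatic BMT patient who receives CEA or CAS is censored by rule. The documents do not say so. They do allow it, and the censoring sentence has no exception. Nothing states that an event found after withdrawal counts in the allocated arm.

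Four further limits stand:

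- If the symptom is itself an ipsilateral ischemic stroke, the primary event is already counted. Only secondary endpoints, such as any stroke or vascular death to 5 years, are then affected.
- A reader might infer that all complications of a late crossover procedure are lost to the primary endpoint. They are not. For BMT the 30-day component runs from randomization (section 6.1), so a later hemorrhagic or contralateral stroke, or a death, is not a primary event under any handling. Only ipsilateral ischemic strokes can be lost.
- Non-adherence and later exclusion criteria can end follow-up in either arm. The direction of that bias is unknown, so the direction of the list as a whole is not established.
- The fall from 80% power is not what the fix would restore, because crossover dilutes the contrast under ITT as well.

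**Conclusion.** The point holds in this form. Section 4.5.1 permits risk-related censoring, specific to BMT in its own example, of later ipsilateral ischemic strokes in patients whose symptoms did not meet the stroke definition. It conflicts with the ITT analysis in section 9.3, is not reconciled with section 5.5, and is inconsistent within itself. For these patients the direction is toward a lower observed BMT rate and a diluted benefit of intervention.

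The size is uncertain. The documents give no q and do not say how often withdrawal would be used. With only about 44 expected BMT events, losing about four (q = 10%) would move the HR to 0.56 and power to 64%. For a given q, that drop from 80% is an upper bound on the harm. If crossover halved risk, censoring would account for about 9 points of power at q = 10% and 21 at q = 20%. The point should be settled in the protocol, because events not observed cannot be recovered at analysis.

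**What to change.** Reword section 4.5.1 to separate two things: stopping or changing the allocated treatment, and leaving the study.

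- A change of treatment, ipsilateral symptoms, non-adherence or a later exclusion criterion does not end follow-up. Visits continue to 5 years.
- All adjudicated primary and secondary endpoint events count in the allocated arm, including those after a change of treatment.
- Censor only at withdrawal of consent, true loss to follow-up or end of study, and at death where death is not an endpoint event.
- Reconcile sections 4.5.1, 5.5 and 9.3, including the two different scopes of withdrawal within 4.5.1.

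The cost is an amendment to the wording. The visits are already scheduled in section 5.1, the sample size does not change, and the clinical care of these patients is not altered.
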